5.1. Schedule of Events

The schedule of events for this study can be found in Table 4 and described in further detail below (see Sections 5.2 to 5.9).

Table 4. Schedule of Events

Event	Screening, enrollment and 12 month (+/- 90 days) FU visit	24 month (+/- 90 days) FU visit	36 month (+/- 90 days) FU visit
GORE® VIABAHN® Endoprosthesis since 15 September, 2012	X		
Inclusion / Exclusion Criteria	X		
Informed Consent Procedure	X		
Medical History	X		
Procedural Information	X		
SAEs and device / procedure related AEs	X	X	X
Clinical Assessment	X	X	X
Re-intervention (if applicable)	X	X	X
Antiplatelet / Anticoagulant Medications	X	X	X
Color Flow Duplex Ultrasound Results (if available)	X	X	X
Angiography Results (if available)	X	X	X

5.2. Informed Consent Process

Each patient that meets the criteria for this evaluation should be informed of any requirements, risks and / or rights for participating in observational data collection. Patients will sign and date a consent form to meet regulatory and / or institutional requirements before data can be entered into the Post-market study. The original signed informed consent form will be retained in the Subject records. A copy of the informed consent document will be given to the patients for their records.

5.3. Pre-Screening / Screening

Patients who received a GORE® VIABAHN® Endoprosthesis for the treatment of PAAs since 15 September, 2012 will be considered for screening for this study. Any screened patient that meets all of the inclusion criteria (Section 4.2) and none of the exclusion criteria (Section 4.3) and has completed a patient information and consent form should be enrolled in this study.

5.4. Enrollment

Patients are considered enrolled if they have met all of the inclusion criteria (Section 4.2) and none of the exclusion criteria (Section 4.3) and have signed the patient information and consent form. Any patient not meeting all of the inclusion criteria and none of the exclusion criteria should be recorded on a screening failure log along with the reason for failure, in addition a screen-failure CRF will be completed. A summary of screen failures including the following information: subject number, date of procedure, and reason for failure will be reported.

Enrollment will be performed in consecutive order beginning with the first patient treated since September 15, 2012. Patients with bilateral PAAs treated with GORE® VIABAHN® Endoprosthesis at different dates can be enrolled in the study. The first limb enrolled will be considered the study limb. Bilateral patients with initial treatment on the same day will not be enrolled. The number of included patients will be monitored via entries in the electronic CRF and Sites will be informed when the inclusion goal (50 patients with data for the 12 month follow-up visit) is met.

5.5. Procedure

As part of the retrospective study the subject previously received the study device. Procedural information related to placement of the device(s) such as overlap, oversizing, number of devices, landing zone, post-deployment dilatation, SAEs, and AEs related to the initial study procedure or the study device will be recorded on the Case Report Forms (CRFs), as available.

5.6. Repeat Interventions

Repeat interventions may take place prior to or after hospital discharge. Procedures taking place during the study procedure should not be captured as repeat intervention. Any available procedural data and angiographic or ultrasound data related to these repeated interventions should be recorded in the CRFs.

5.7. Follow-Up

Follow-up visits need to be done in a window of +/- 90 days in order to be documented as study visits. This means that 12 month follow-up visit needs to take place between 275 and 455 days post-procedure, the 24 months follow-up visit between 640 and 820 days post-procedure, and the 36 month follow-up visit between 1005 and 1185 days post-procedure. All visits occurring from the time of procedure through 1185 days post-procedure should be recorded for each subject. If a subject had an office visit between 1005-1185 (three years \pm 90) days post-procedure, then no further information will be collected on the subject after 1185 days. Device or procedure related AEs, antiplatelet / anticoagulant medications, clinical assessment, ultrasound, and angiographic information should be collected, during each follow-up visit as applicable and available.

5.7.1. SAEs and device or procedure related AEs

SAES and device or procedure related AEs found in the subject chart should be recorded at each follow-up visit. Additional details regarding AE recording can be found in Section 9.

5.7.2. Medications

Medications being recorded for this study include post-procedural antiplatelet and anticoagulation medications. Start date, end date, dose, and frequency should be recorded for each subject. Medications used during the procedure such as intravenous Heparin do not need to be recorded.

5.7.3. Clinical Assessment

Clinical Assessments include the presence of palpable pedal pulses and an Ankle Brachial Index (ABI). The ABI of each subject should be recorded. A Toe Brachial Index may not be used in place of an ABI.

5.7.4. Color Flow Duplex Ultrasound

When possible Color Flow Duplex Ultrasound information should be recorded for each subject at each study visit; verification of the presence or absence of blood flow should be recorded. Additionally, aneurysmal dimensions will be evaluated.

5.8. Subject Withdrawal from the Clinical Study

All patients have the right to withdraw themselves from participation at any point during the study. In addition, Principal Investigators also have the authorization to terminate a subject's participation in the study.

A description of the reason for the subject's termination will be documented. Reasons for termination include: completion of study, subject's voluntary withdrawal, physician-directed subject withdrawal, and death.

Upon study exit the subject will be followed per standard of care by Investigator and / or another physician.

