8.2. Minimization of Risks

Potential risks associated with the use of the GORE® VIABAHN® Endoprosthesis may be minimized by the following activities:

- The Sponsor has performed qualification testing on the device and device components, and appropriate quality control measures have been implemented in production;
- Investigators will be selected who are knowledgeable and experienced in interventional radiology procedures, and vascular anatomy;
- The Site Investigator, Sub-Investigators, Clinical Study Coordinator(s) or designee at each Site will be trained to the protocol;
- Protocol inclusion / exclusion criteria are designed to select appropriate patients and identify potential complications;
- Data completed by the Sites will be monitored to evaluate protocol compliance, data accuracy and subject safety; and
- Safety and performance data obtained during the clinical study will be shared with the Site Investigators to aid understanding of the device and potential complications associated with its use.

However, there is no risk to the patient by participating in this retrospective study because the procedure has already been performed and no additional procedures are requested except hospital standard of care.

[REDACTED]

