8.4. Risk-to-Benefit Rationale

CONFIDENTIAL INFORMATION

MD133246 Protocol Template
Revision#: 1
Doc Type: GC

This study does not lead to any change in patient management and patients will receive the same treatment as they would have received if they had decided not to participate. Therefore, there is neither an additional risk nor a direct benefit related to the participation in the study.

9. Adverse Events and Safety Monitoring

AEs are defined as any untoward medical occurrences, unintended disease or injury or any untoward clinical signs (including abnormal laboratory findings) in patients, users or other persons whether or not related to the investigational medical device.[56] According to the primary and secondary endpoints of this study, the documentation of adverse events will concern all serious adverse events and adverse events related to the initial study procedure or the study device, regardless of the severity throughout 36 months.

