9.1.3. Adverse Event Reporting and Coding

AEs will be reported on the appropriate CRF for that visit and documented in the subject's permanent medical record. The Investigator at each Site is ultimately responsible for reporting AEs to the Sponsor. The Investigator shall supply the Sponsor with any additional requested information.

Timely and complete reporting of safety information assists the Sponsor in identifying any untoward medical occurrence, thereby allowing: (1) protection of safety of study patients; (2) a greater understanding of the overall safety profile of the GORE® VIABAHN® Endoprosthesis; (3) appropriate modification of study protocols; and (4) adherence to worldwide regulatory requirements.

The following information should be collected for each reported AE:

- AE Name
- AE Onset Date
- Relationship
- Classification (serious / non-serious)
- Treatment
- Outcome
- Resolution Date

All reported AEs will be coded using the Medical Dictionary for Regulatory Activities (MedDRA).

In reporting AEs the following submission guidelines should be followed:

- AE reporting begins once the subject has received a GORE® VIABAHN® Endoprosthesis and continues until study completion / discontinuation.
 - NOTE: Any AE that occurs while the subject is in the operating room / catheterization laboratory should not be recorded as an AE, unless it is unresolved when the subject leaves the operating room / catheterization laboratory.
 - NOTE: Any AE occurring after the final study visit will not be recorded in this study.
- AEs with an outcome status of "Ongoing" should be assessed at each follow-up evaluation to determine if the event has resolved. AEs ongoing at study completion / discontinuation should be left as "Ongoing" on the AE CRF.

CONFIDENTIAL INFORMATION

MD133246 Protocol Template

Revision#: 1

Doc Type: GC

- Clinical sequelae present at baseline should be recorded on the Medical History CRF. If the clinical sequela increases in severity or frequency from baseline then it should be reported as an AE.
- If known, the diagnosis of the underlying illness or disorder should be recorded, rather than its individual symptoms. If unable to provide a diagnosis, report the symptoms as separate events. AEs should be reported using the full name without abbreviations or narratives.

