- Subject Completion/Discontinuation (Completion/Discontinuation [Surgical bypass, Amputation above the metatarsal, Lost to follow-up, Death, Other])
- Repeat Interventions Summary (Days to First Intervention, Reason for Reintervention, Endoleak at Time of Intervention [Endoleak, Type], Type of Reintervention Performed, Successful Reintervention, ABI at Discharge)

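### Investigators may end a subject's participation with no defined grounds, and outcomes after that exit are not collected, so an exit linked to impending failure could flatter mainly the 24- and 36-month results

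*Protocol*

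**What the plan says.** Protocol 5.8, after giving subjects the right to withdraw, states: "In addition, Principal Investigators also have the authorization to terminate" a subject's participation. It sets no criteria for using this authority. It does require a record: "A description of the reason for the subject's termination will be documented". The reasons it names are these: "Reasons for termination include: completion of study, subject's voluntary withdrawal, physician-directed subject withdrawal, and death". The physician-directed entry tells the reader who decided, not why. Section 5.9 also requires the reason on the CRF. After exit, section 5.8 leaves the subject to standard-of-care follow-up.

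On data after exit, Protocol 9.1.3 says that AE reporting "continues until study completion / discontinuation". No passage says that patency, re-intervention, amputation or death continues to be abstracted from the chart.

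On what participation means for the patient, section 8.2 says "there is no risk to the patient by participating in this retrospective study because the procedure has already been performed", and section 8.4 says "This study does not lead to any change in patient management".

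The discontinuation table in SAP 8.1 has these categories: "Completion/Discontinuation [Surgical bypass, Amputation above the metatarsal, Lost to follow-up, Death, Other". SAP 8.2 plans a listing of completion and discontinuation data and a listing of reasons for early termination. SAP 5.2 includes all enrolled patients in the analysis. SAP 5.4 and 5.5 give no rule for a missing 12-month patency status, no censoring rule for withdrawals and no sensitivity analysis for them.

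**The concern.** A rule that lets the investigator take a subject out of a study usually protects the subject from a study treatment or procedure. This study has none: the implant is done and care is standard of care. An investigator-directed exit leaves the patient's management unchanged, and what it ends is the collection of data.

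The decision lies with the site investigator, who knows the limb's course in an unblinded single-arm study. If a subject leaves because the limb is deteriorating, and leaves before an occlusion, re-intervention or amputation is recorded, the exit is informative. Patency and freedom from limb loss or re-intervention would then be overstated, and event counts understated. An exit of this kind complies with the protocol, so the bias control in Protocol 10.4, which rests on adherence to eligibility and protocol, would not flag it.

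**Working it through.** **No planned figure to reproduce.** The documents give no withdrawal rate, and the hypothesis and sample-size text is redacted. The figures below are illustrations.

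**Which endpoints are exposed**

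- Inclusion is retrospective and follow-up can be prospective (Protocol 3.2). Screening, enrollment and the 12-month visit share one column of the schedule (Protocol 5.1, Table 4).
- Treatment dates run from 15 September 2012 and enrollment was expected from March to December 2015 (Protocol 5.12). Many 12-month outcomes were therefore probably in the chart at consent, where a later exit cannot hide them.
- Section 5.12 expects the last primary endpoint follow-up by the end of 2017, after enrollment closes. Some 12-month visits can therefore be prospective and are exposed.
- The 24- and 36-month visits lie later still, so the exposure is mainly there.

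**12-month patency.** Assume 50 limbs of which 6 truly fail, so 44 are patent. The implied 88% lies inside the 79 to 100% range in SAP 2.5. Let *k* be the number of failing limbs that exit before the failure is recorded. The plan does not say which of these conventions applies:

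| k | Dropped: 44/(50 − k) | Replaced until 50 have data: (44 + 0.88k)/50 | Kept as non-success: 44/50 |
|---|---|---|---|
| 0 | 88.0% | 88.0% | 88.0% |
| 1 | 44/49 = 89.8% | 44.88/50 = 89.8% | 88.0% |
| 2 | 44/48 = 91.7% | 45.76/50 = 91.5% | 88.0% |
| 3 | 44/47 = 93.6% | 46.64/50 = 93.3% | 88.0% |

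The second convention is the expected value if each replacement has an 88% chance of patency. It is included because enrollment runs until 50 subjects have 12-month data (Protocol 3.2) and the no-replacement rule covers only losses after that visit (SAP 5.1). Under the first two conventions each removed failure adds just under 2 points; under the third it adds nothing.

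**12 to 36 months.** Assume 40 limbs at risk at 12 months, 6 failing by 36 months, no other losses, and *k* of the 6 censored before any failure is recorded. The conditional Kaplan-Meier estimate is then 34/(40 − k):

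- k = 0: 34/40 = 85.0%
- k = 1: 34/39 = 87.2%
- k = 2: 34/38 = 89.5%
- k = 3: 34/37 = 91.9%

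Each removed failure adds about 2.2 to 2.4 points. Censoring at exit is an assumption here, since the SAP states no such rule.

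**Safety.** Protocol 10.3.4 and 10.3.5 report counts. An event after exit is not reported (section 9.1.3), so it is missing from the count whatever denominator is used.

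**The case against.** Several points count against a stronger reading.

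- *A reader might infer that a subject can be removed without any reason.* The documents do not support that. The reason must be described (5.8), marked on the CRF (5.9) and listed (SAP 8.2). In a study of about 50 subjects a listing shows each case. What is missing is a set of permitted grounds. This stands, but a listing shows that someone left and does not recover the outcome.
- *A reader might infer that the results are biased.* Bias needs an exit that is related to impending failure and that comes before the failure is recorded. Events recorded before exit still count, and nothing deletes them. The documents give no sign of how often such exits occur.
- *A reader might take 89.8 to 93.6% as the bias in the primary endpoint.* Those figures need a rule the plan does not state. SAP 5.2 includes all enrolled patients, and SAP 5.4 requires patency at the one-year visit for a success, so a withdrawn limb can be read as a non-success in the denominator. SAP 5.5 omits unknown status expressly only for length of stay, procedure length and technical success. The text does not settle it: SAP 8.2 also plans a listing of enrolled patients excluded from the analysis population.
- *A reader might conclude that the authority serves no purpose and should be deleted.* That goes too far. Defective consent or ineligibility discovered later are possible grounds unrelated to risk, and Protocol 11.2 makes the investigator responsible for patients' rights and welfare.
- Protocol 5.7 asks for all visits through day 1185 to be recorded for each subject, section 6.2.2 requires verification to source, and section 10.4 provides for audits. These constrain selective recording during participation. None says that recording continues after exit, and section 9.1.3 says that AE reporting does not.

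**Conclusion.** The point holds in a limited form. Protocol 5.8 gives an open authority to end participation in a study that adds no risk, and exit stops AE reporting without any provision for collecting other outcomes. An exit linked to impending failure could therefore bias results favourably. The exposure is mainly to patency, limb loss, re-intervention and serious adverse event counts at 24 and 36 months, and to those 12-month visits that are prospective.

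The size is conditional. With 6 true failures in 50, each failure removed before it is recorded adds about 2 points at 12 months if the limb is dropped or replaced, and nothing if it stays in as a non-success. From 12 to 36 months it adds a little over 2 points, assuming 40 at risk, 6 failures and censoring at exit. With no such exits there is no bias, and the documents do not show whether there will be any.

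**What to change.** In Protocol 5.8 and 9.1.3, state that after an investigator-directed discontinuation, chart data on patency, re-intervention, amputation, SAEs, device- or procedure-related AEs and death continue to be collected to day 1185 unless the subject withdraws consent. The authority itself can stay.

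In the SAP 8.1 discontinuation table, report physician-directed and subject withdrawals separately, each with last known patency status, rather than under Other. This makes such exits visible, but only continued collection recovers the outcome.

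The cost is a little more chart abstraction, with no extra visits and no change in care. The amendment goes to the CCTIRS and CNIL, as Protocol 6.5 requires for any amendment.

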5.9. Subject Study Completion

A subject has completed the study when 36 months (1185 days or 3x365 + 90 days) of follow-up data has been recorded on the CRFs. Any subject that does not complete these requirements due to voluntary withdrawal, death, lost secondary patency (e.g. had a study limb bypass) or any other reason will be considered a withdrawal and the reason for discontinuation will be marked on the CRF.

If a subject is lost to follow-up, the appropriate CRF must be completed as soon as possible after subject status has been determined. If a subject fails to comply with follow-up evaluations, the Site must make at least three attempts to contact the patient and his family and potentially his General Practitioner. Each attempt to contact the subject and the method used (e.g., telephone contact, registered letter) must be documented in the subject's records.

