## 4.0 Study Data Collection

### 4.1 Study Data Collection Intervals and Windows

Follow-up visits are scheduled for 12 months, 24 months, and 36 months after the procedure. The visits need to be done in a window of +/- 90 days in order to be documented as study visits. The visit windows are shown in Table 1.

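### Protocol 5.7, 5.9 and 9.1.3 give inconsistent ends of follow-up, so the 36-month adverse-event counts have no common end date and can stop up to 90 days short of day 1095

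*Protocol*

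**What the plan says.** Four rules bear on when a subject's follow-up ends.

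- **Visit window.** Protocol 5.7 places "the 36 month follow-up visit between 1005 and 1185 days post-procedure". SAP 4.1 repeats the rule ("The visits need to be done in a window of +/- 90 days in order to be documented as study visits"), and SAP Table 1 gives the same days.
- **Data collection.** Protocol 5.7 also says "All visits occurring from the time of procedure through 1185 days post-procedure should be recorded for each subject". For a subject seen inside the 36-month window it adds "then no further information will be collected on the subject after 1185 days".
- **Completion.** Under Protocol 5.9 a subject has "completed the study when 36 months (1185 days or 3x365 + 90 days) of follow-up data has been recorded". A subject who falls short through voluntary withdrawal, death, lost secondary patency "or any other reason will be considered a withdrawal and the reason for discontinuation will be marked on the CRF".
- **AE recording.** Protocol 9.1.3 runs AE reporting from receipt of the device to completion or discontinuation. A note beneath that rule says "Any AE occurring after the final study visit will not be recorded in this study". The final study visit is not defined.

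The opening of Protocol section 9 asks for serious and related AEs over the full 36 months. SAP 5.5 tabulates counts at 24 and 36 months and names no onset-day cut-off. Completion status feeds one SAP 8.1 table, "Subject Completion/Discontinuation (Completion/Discontinuation [Surgical bypass, Amputation above the metatarsal, Lost to follow-up, Death, Other", and a listing in SAP 8.2.

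**The concern.** Day 1185 is the last day of the 36-month window, not 36 months. A subject with a valid visit on day 1050 and nothing afterwards meets the visit rule, but on a literal reading does not meet the completion rule. The same subject is caught between the two AE rules: one continues until completion, the other stops at the visit.

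Two outputs are exposed. The first is the 36-month count of serious and related AEs, a secondary endpoint in a study whose stated aim is long-term safety. The counts are not adjusted for time observed. If recording stops at the visit, each subject contributes a period set by when the hospital happened to schedule the appointment. The second is the completion table, where an event-free subject short of day 1185 has nowhere to go but the category Other. Voluntary and physician-directed withdrawals (Protocol 5.8) would fall there too, having no category of their own.

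**Working it through.** **Inputs.** Completion threshold 1185 days (Protocol 5.9). Window 1005 to 1185 (Protocol 5.7, SAP Table 1). Target 50 patients (Protocol 3.2). Nominal 36 months is taken as 3 × 365 = 1095, the centre of the window; neither document states it as an end of follow-up. The documents give no distribution of visit dates, so the averages below rest on assumed ones.

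**The plan's own figures.** 3 × 365 + 90 = 1185, as stated. The windows reproduce as y × 365 ± 90: 275–455, 640–820 and 1005–1185.

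**Distance between the two AE end points.** If completion means day 1185 and the final study visit is the 36-month visit, the difference is 1185 − d for a visit on day d. The maximum is 1185 − 1005 = 180 days.

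**Shortfall to day 1095 if the note is followed and the 36-month visit is the last.** The loss is max(0, 1095 − d).

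- The window holds 1185 − 1005 + 1 = 181 days. Days 1005 to 1094 number 90, so 90/181 = 49.7% of visit days are affected.
- Maximum loss: 1095 − 1005 = 90 days, or 90/1095 = 8.2%.
- Total loss over the window: 90 + 89 + … + 1 = 90 × 91/2 = 4,095 days.
- Uniform visits, affected subjects: 4,095/90 = 45.5 days on average.
- Uniform visits, all subjects: 4,095/181 = 22.6 days, or 22.6/1095 = 2.1%.
- For 50 patients who all reach the visit: 50 × 22.6/365.25 = 3.1 of 50 × 1095/365.25 = 149.9 person-years.

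If visits cluster normally around day 1095 within the window:

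| SD of visit day | Seen before day 1095 | Mean loss, all subjects |
|---|---|---|
| 15 days | 48.6% | 6.0 days |
| 30 days | 49.3% | 11.8 days |
| 45 days | 49.5% | 16.3 days |

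Subjects seen after day 1095 err the other way. With no cut-off in SAP 5.5, up to 90 days beyond 36 months can enter their counts.

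**Completion.** If data end at the 36-month visit, only day 1185 satisfies 5.9, which is 1 of 181 valid days (0.6%). If visits and chart data are kept through day 1185, as 5.7 instructs, all 181 days can lead to completion. The 0.6% is therefore the bound under the strictest reading and not an expected rate.

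**The case against.** The best defence is that Protocol 5.7 answers most of this. Collection closes at day 1185, not at the visit, and 5.9 uses the same day as the close of the data window. AE reporting until completion then also means day 1185, and Protocol 5.7.1 takes events from the chart. On that reading a subject seen on day 1005 can complete, and the AE gap is small or nil.

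This stands in part. It rules out the stronger inference a reader might draw, that nearly every valid completer will be recorded as a withdrawal and true attrition hidden. That follows only if nothing is recorded after the visit, which 5.7 does not say. Bypass, amputation, loss to follow-up and death also have their own categories in the table, and SAP 8.2 lists reasons for early termination.

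It does not remove the conflict over AEs. The Protocol 5.1 schedule has nothing after the 36-month visit, 5.7.1 ties AE recording to follow-up visits, and no step reopens the chart between that visit and day 1185. The note in 9.1.3 still tells a site to leave out later events. Sites can follow either rule in good faith.

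The consequence is limited. SAP 5.2 analyses all enrolled patients whatever their completion status. Patency, limb loss and repeat intervention at 36 months are time-to-event endpoints, where unequal follow-up enters as censoring. Raw AE counts have no such protection.

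**Conclusion.** The point holds as an inconsistency that should be fixed, with modest consequences. The visit, completion and AE rules do not share an end date, the two AE rules in Protocol 9.1.3 can differ by up to 180 days, and SAP 5.5 does not settle which events count at 36 months.

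The shortfall in the counts is conditional: the note must be followed and the 36-month visit must be the last. It then affects only subjects seen on days 1005 to 1094, and by no more than 90 days each. Averaged over all subjects it is about 23 days under uniform visits and 6 to 16 days under clustered ones. The 180-day figure is not the loss to 36 months; it would be the largest loss only if 36 months were read as day 1185.

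Mislabelling event-free subjects as withdrawals is a risk of the literal text of 5.9 and cannot be predicted from the documents. The 12-month primary endpoints are untouched.

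**What to change.** 1. **Protocol 5.9:** define completion as a documented 36-month visit within days 1005 to 1185.
2. **Protocol 9.1.3:** replace the note with one AE end date, the same for every subject who has not died or withdrawn earlier, that covers at least day 1095. Day 1185 would match the collection limit in 5.7. Point the parent reporting rule to the same date, and add a chart check before final database lock.
3. **SAP 5.5:** state one onset-day cut-off for the 36-month counts, for example day 1095, and list later events separately.

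With an AE end date of day 1185, the gap between the two AE rules falls from up to 180 days to 0. With a count cut-off at day 1095 and recording at least to that day, the shortfall falls from up to 90 days to 0.

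The cost is a few sentences and one closing chart check for subjects seen before the AE end date. The later the chosen date, the more subjects need the check. No visit or procedure is added.
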